STUDY TITLE	A non-interventional, open observational non-inferiority study in two cluster- assigned cohorts of children aged 14 months into the safety of NeisVac-C® vaccines manufactured at two different production sites and given simultaneously with measles-mumps-rubella vaccine, assessed by web-based intensive monitoring
STUDY NAME	Peuterprik
STUDY PRODUCT(S)	NeisVac-C®, Meningococcal Group C Polysaccharide Conjugate Vaccine Adsorbed, 'old' and 'new'
STUDY PHASE	Post marketing surveillance
STUDY OBJECTIVES	To compare the safety of the NeisVac-C® bulk material produced at Baxter in Orth/Donau (new) (group A) with the material produced in Beltsville (old) (group B) in toddlers aged 14 months, administered simultaneously with MMR vaccine.
Primary	The primary endpoint is the proportions of subjects with fever reactions within 4 days after administration.
Secondary	The secondary endpoints are proportions of subjects with 
 - solicited other systemic and local reactions within 4 days after administration - non-solicited other systemic and local reactions within 4 days after administration - non-solicited other systemic and local reactions from 5 to 28 days after administration
STUDY DESIGN	non-interventional, open observational non-inferiority study with two cluster- assigned cohorts
SUBJECTS	At least 2430 healthy toddlers aged 13-18 months old, eligible to receive MenC and MMR vaccinations according to the NIP
INCLUSION CRITERIA	
 - age 13-18 months old (boundaries included) - eligible to receive MenC and MMR vaccinations according to the NIP
EXCLUSION CRITERIA	
 - children receiving either MenC or MMR vaccine and not both at same time - children with parents that are not able or willing to understand or fill the questionnaires
STUDY PARAMETERS	Primary: reactogenicity defined as % of children with rectal temperature 38,0 Celsius and above during the first 4 days after vaccination Secondary: other solicited and unsolicited complaints and symptoms at injection site as well as systemic reactogenicity
STUDY GROUPS	Two study groups of similar size will be formed according to the MenC vaccination that has been given at the baby clinics, i.e. NeisVac-C® from either Orth/Donau (group A) of Beltsville (group B).
STUDY PRODUCT REGIME	Children receive one injection of either MenC vaccine while MMR vaccine is given at a different injection site simultaneously
STUDY PERIOD	one year
STUDY DESCRIPTION	non-interventional, open observational non-inferiority study with two cluster- assigned cohorts
STATISTICAL ANALYSIS	The primary endpoint of the study, fever cases observed within 4 days after vaccination will be analyzed using logistic regression with vaccination groups ("old" / "new" product) and potential confounders as explanatory factors, applying a log link in order to obtain relative risk estimates at the end. Relative risk and its 95% CI of occurrence of fever cases with the "new" and "old" NeisVac-C® product will be calculated from the regression model assessing a potential increase of fever reactions with the "new" product. If the upper limit of the 95% CI is below 1.5 then the "new" product is considered to be non-inferior to the old one as far as fever reaction is concerned. The secondary endpoints will be analyzed similarly and descriptive without the non-inferiority considerations.
SPONSOR	Lareb

ABBREVIATIONS

Term	Explanation
AE	Adverse events
CI	Confidence Interval
CRF	Case Report Form
DVP	Dienst Vaccinvoorziening en Preventieprogramma's (till 2013 termed Regionale Coördinatie Programmas RCP), i.e. regional vaccine distribution and registry (part of RIVM)
ENCEPP	European Network of Centres for Pharmacoepidemiology and Pharmacovigilance
GCP	Good Clinical Practice
ICF	Informed Consent Form
ICH	International Conference on Harmonisation
ITT	Intention to treat
MenC	NeisVac-C® vaccine to prevent infections by meningococci group C
MHRA	Medicines and Healthcare products Regulatory Agency
MMR	M-M-R-VaxPro® vaccine to prevent measles-mumps-rubella
NIP	Netherlands/National Immunisation Programme
PP	Per protocol
RIVM	Rijksinstituut voor Volksgezondheid en Milieu (National Institute of Public Health and Environment)
RMP	Risk Management Plan
RMS	Reference Member State
RVP	Rijksvaccinatieprogramma (National Immunisation Programme)
SAE	Serious adverse events
s.d.	Standard deviation
SmPC	Summary of Product Characteristics
SSAR	Suspected Serious Adverse Reaction
SUSAR	Suspected Unexpected Serious Adverse Reaction

TABLE OF CONTENTS

TITLE PAGE

PROTOCOL SIGNATURE PAGE

PROTOCOL SYNOPSIS

ABBREVIATIONS

TABLE OF CONTENTS

CHAPTER 1. INTRODUCTION

1.1 Rationale for the study

NeisVac-C® is a meningococcal group C polysaccharide conjugate vaccine (tetanus toxoid protein conjugate). The vaccine stimulates the immune system to produce antibodies against group C meningococcal bacteria, thereby preventing the development of meningitis/meningococcal disease. It is indicated for active immunisation of children aged 2 months and older, adolescents and adults, for the prevention of invasive disease caused by *Neisseria meningitidis* serogroup C.

NeisVac-C® is a product of Baxter Ltd. Due to a transfer of the manufacturing site of the drug substance from Baxter's facility at Beltsville, Maryland, USA to Baxter's facility at Orth/Donau, Austria, Baxter has applied for a Type II variation application (UK/H/0435/001/11/047/G) to allow release of Orth/Donau batches based on comparability to clinically qualified Beltsville batches to the United Kingdom's Medicines and Healthcare Products Regulatory Agency (MHRA) as the authority of the Reference Member State (RMS). Baxter was also requested by the MHRA to submit a Risk Management Plan (RMP) in which it should be considered how the safety and efficacy of the vaccine manufactured at the new Orth/Donau site would be actively monitored in comparison with the Beltsville vaccine. In particular it was asked to consider the extent to which there would be co-marketing of the vaccines and to specifically address batch traceability, the limitations of passive surveillance to evaluate relative reactogenicity and to formulate proposals to either overcome this or to conduct active surveillance to demonstrate comparable reactogenicity.

In The Netherlands Immunisation Programme NeisVac-C® is given to children of an age of about 14 months simultaneously with MMR vaccine. MMR is a live, attenuated virus vaccine, with a latency window of about 5 days for side effects that are associated with the replication of vaccine viruses. Any febrile reaction occurring during the first 4 days after administration of both vaccines, is more likely to be associated with NeisVac-C® than with MMR vaccine. Because of this co-administration, The Netherlands is a suitable country where reactogenicity of NeisVac-C® can be evaluated, compared to countries where NeisVac-C® is co-administered with non-live vaccines (as is the case with most other European countries).

We therefore will investigate systemic and local adverse events following NeisVac-C® and MMR administered simultaneously, with emphasis on the first 4 days after administration, and with subsequent follow-up during the remaining month.

CHAPTER 2. STUDY OBJECTIVES

2.1 Primary study objective

The primary objective of this study in children aged 14 months is:

- to compare the proportions of vaccinees with fever of $\geq 38^{\circ}\text{C}$ within 4 days after injections of the Baxter NeisVac-C® vaccine bulk material produced in Orth/Donau (new, group A) or NeisVac-C® vaccine of which the bulk material was produced in Beltsville (old, group B), and simultaneous MMR vaccine for both groups of NeisVac-C® recipients.

2.2 Secondary study objective(s)

Secondary objective of this study is to investigate

- the safety profile with other parameters (solicited and non-solicited) within 4 days after simultaneous injections of either MenC, and MMR vaccines.
- the safety profile of these vaccines with non-solicited parameters from 5 to 28 days after injection.

CHAPTER 3. STUDY DESIGN

3.1 Study design

This is a non-interventional, open observational non-inferiority study with two cluster- assigned cohorts .

3.2 Study description

Toddlers (14 months old) will receive at vaccination centers NeisVac-C® vaccination with either

- “old” lots produced in Beltsville (group B), or
- “new” lots from Orth/Donau (group A), simultaneously with MMR vaccine.

From 4 full days after the vaccines were administered, parents will receive web-based questionnaires with questions about any ADRs that occurred after vaccination.

The 1st questionnaire is sent at day 5 and covers days 1, 2, 3 and 4.

The 2nd questionnaire will be sent after two weeks and covers days 5 to 14.

The 3rd questionnaire will be sent after four weeks and covers days 15 to 28.

Day numbers are defined as:

- Day 1: day of vaccination, e.g. Monday
- Day 2: 1st day after vaccination, e.g. Tuesday
- Day 3: 2nd day after vaccination , e.g. Wednesday
- Day 4: 3rd day after vaccination, e.g. Thursday = last day of fever counting for primary endpoint.
- Day 5: 4th day after vaccination, e.g. Friday

3.3 Duration of the study and milestones

The study will continue for a whole year, to cover all seasons, and multiple vaccine batches as supplied by Baxter Ltd. The duration of the study for each participant is approximately one month from vaccination.

Proposed timing of events (dependent on availability of study products and schedules of their delivery by RIVM). In case of vaccine batches to be studied run out of their period of approved use or pass their expiry date, the study may stop earlier.

year	month	activity / step
2014	APR	delivery of the appropriate batches in the study area
2014	APR	sending letters to parents of eligible children, from start weekly letters
2014	MAY	first inclusions
2014	JUN	first fully completed questionnaires
2015	APR	last letters sent
2015	MAY	last inclusions
2015	JUN	last completed questionnaires
2015	SEP	final draft study report
2015	OCT	study report

CHAPTER 4. SUBJECTS

4.1 Study population

Participants will be recruited from a regionally defined population of healthy children who are eligible to receive regular vaccinations with MenC and MMR vaccines according to the Netherlands Immunisation Programme.

In this study at least 2430 fully evaluable toddlers, aged 14 months, equally distributed between the 'old' and the 'new' MenC vaccine who are vaccinated with simultaneous MMR vaccine according to the Dutch Immunization Programme in clinics are required for Per Protocol analysis.

4.2 Inclusion criteria

- children 14 months old (age range 13-18 months; boundaries included) who receive the NeisVac-C® and MMR vaccination in one of the participating clinics according to the NIP

4.3 Exclusion criteria

- children receiving either MenC or MMR vaccine and not both at the same time
- children that have received simultaneously any other vaccine than MenC and MMR
- children that are vaccinated at baby clinics that do not participate in the study
- children whose parents/caretakers register for the study later than day 4 after vaccination.
- children with parents that are not able or willing to understand/fill the questionnaires in Dutch.

4.4 Subject recruitment

In the target region designated vaccination centers/baby clinics will be supplied with NeisVac-C® vaccines with either "old" lots produced in Beltsville or "new" lots from Orth/Donau.

Approximately one month before the scheduled vaccination (usually at age 14 months) the parents/caretakers of children in the target region, will receive a letter with information about the study and the possibility to already sign up for the study, both online and through a paper form.

At the baby clinic, following NeisVac-C® and MMR vaccination, parents will be asked to participate, and the information required for participation will be written down on the study flyer (specification of injection sites and batch number per vaccine). Based on information in the letter and subsequent flyer, parents may decide to participate and register at the study web-page. Parental consent is considered a valid equivalent of a signature if they voluntarily ticked a box stating that they have understood all information and confirm their participation.

4.5 Instructions and technical assistance during the study

During the study, the parents may contact the Netherlands Pharmacovigilance Centre Lareb at any time through mail or telephone if they have any questions concerning the study, especially if technical assistance in filling the questionnaires is required.

4.6 Subject discontinuation during the study

The participant can withdraw from the study at any moment without stating a reason. If a questionnaire has not been completed after a reminder has been sent, the patient is considered lost to follow up and will not receive any further questionnaires. Discontinuation has no medical consequences for the participant.

CHAPTER 5. STUDY PARAMETERS

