6.4 Reminders

Parents are sent reminders if the filled questionnaire is not received by Lareb.

- after Q1 (day 5), reminder at day 7, valid time of return: day 8
- after Q2 (day 14), reminder at day 16, valid time of return: day 18
- after Q3 (day 28), reminder at day 32, valid time of return: day 36.

Questionnaires received after the valid time of return will not be included in the Per Protocol analysis.

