8.2 Randomization and stratification

Central randomisation: baby clinics are randomly assigned to use either the old or the new NeisVac-C®. Shipments are done according to a distribution list, generated to randomly assign either batch to any participating baby clinic, to ensure that both groups are similar in size, and that local differences in confounding factors (e.g. concurrent infections, habits and attitudes towards vaccinations, ...etc) are balanced out.

RIVM/DVP will generate the distribution list, and will provide the baby clinics accordingly (Appendix 2).

8.3 Study size and recruitment population.

In order to evaluate 1215 children per group according to protocol (see paragraph 9.2) we need to recruit higher numbers of children. The following estimations are done to determine the population size to target for participation. With 1215 per group we need 2430 fully evaluable and complete datasets. We assume that 90% of data from an estimated 2700 respondents that have completed all questionnaires are evaluable. We assume that after starting the questionnaires 75% of responders will also complete the last questionnaire, thus giving an estimation of 3600 responding parents that start and agree to participation. Experience of RIVM indicates that about 40% of parents participate to a similar questionnaire proposal. However, to be sure to include the desired number of respondents we assume a lower percentage: 15-20%. Thus we assume that 18.000 to 24.000 parents need to be addressed for taking part in the investigation. In addition, to compensate for other interferences or loss, we intend to address 25.000 parents.

8.4 (Un) blinding procedure

Not applicable

CHAPTER 9. STATISTICS

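### Section 4.6 stops questionnaires to families that have not withdrawn after one unanswered form, without a cut-off day, and needlessly thins the day 5-28 data

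*Protocol*

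**What the plan says.** Section 4.6 states the trigger, "If a questionnaire has not been completed after a reminder has been sent", and the consequence, "the patient is considered lost to follow up and will not receive any further questionnaires". It names no day after the reminder on which the rule takes effect.

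Section 6.4 gives the timetable. For the first questionnaire it reads "after Q1 (day 5), reminder at day 7, valid time of return: day 8". The second form goes out on day 14, is followed up on day 16 and counts as on time up to day 18. For the third, the corresponding days are 28, 32 and 36.

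The same section states what lateness costs: "Questionnaires received after the valid time of return will not be included in the Per Protocol analysis". It mentions no other consequence.

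Section 2.2 makes "the safety profile of these vaccines with non-solicited parameters from 5 to 28 days after injection" a secondary objective. Under section 3.2, questionnaire 2 (Q2) covers days 5 to 14 and questionnaire 3 (Q3) covers days 15 to 28. Section 8.3 assumes that "75% of responders will also complete the last questionnaire".

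**The concern.** A family that leaves one form unanswered has not asked to leave the study, yet the study ends its own contact with it. Q2 and Q3 are the only active source for days 5 to 28, so the missing data are partly of the study's own making.

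Two features make this matter here. First, section 1.1 explains that the regulator asked the manufacturer to address the limits of passive surveillance or to survey actively. A family cut off under 4.6 falls back to passive reporting. Second, section 9.1 cites an earlier Dutch study in which fever rose from day 5 to 19% at day 9. The first period forfeited after a missed questionnaire 1 (Q1) is therefore one in which the protocol itself expects many events.

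At stake are the completeness of a secondary safety endpoint and the active search for serious events after day 4.

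**Working it through.** **1. The two rules side by side.** Time from sending to valid return, and from reminder to valid return, from section 6.4:

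- Q1: 8 − 5 = 3 days; 8 − 7 = 1 day
- Q2: 18 − 14 = 4 days; 18 − 16 = 2 days
- Q3: 36 − 28 = 8 days; 36 − 32 = 4 days

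Take a Q1 returned on day 9. Section 6.4 keeps it out of the Per Protocol analysis but says nothing against sending Q2 on day 14. Under section 4.6 the family may or may not already be lost to follow-up, because no cut-off is given. The text does not settle the case.

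**2. What the rule takes away depends on which form is missed.**

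- Q1 missed: Q2 and Q3 are not sent, so all of days 5-28 goes unasked.
- Q2 missed: Q3 is not sent, so days 15-28 go unasked. The family's gap for days 5-14 is its own.
- Q3 missed: nothing further is withheld.

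**3. The plan's own figures (section 8.3) reproduce.**

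- 2430 / 0.90 = 2700 respondents with all questionnaires completed
- 2700 / 0.75 = 3600 starters
- Planned loss: 3600 − 2700 = 900, and 900 / 3600 = 25%

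**4. Families from whom the rule withholds a form.** The plan does not split the 900 by questionnaire, so a split has to be assumed.

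(a) Equal proportional loss at Q1, Q2 and Q3. Completion per form is 0.75^(1/3) = 0.9086.

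- After Q1: 3600 × 0.9086 = 3271, so about 329 are lost (9% of 3600) and receive neither later form.
- After Q2: 3600 × 0.9086² = 2972, so about 299 more are lost and are not sent Q3.
- After Q3: 2700, so about 272 more are lost, from whom the rule takes nothing.
- Denied at least one form: 329 + 299 = 628, and 628 / 3600 = 17%.

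(b) Every starter completes Q1, with equal proportional loss at Q2 and Q3. Completion per form is 0.75^(1/2) = 0.8660. After Q2, 3600 × 0.8660 = 3118 remain, so about 482 are not sent Q3. Nobody loses the whole of days 5-28 through the rule.

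(c) Extremes: 900 if all are lost at Q1, 0 if all are lost at Q3.

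**5. What could be regained under (a).** The protocol gives no rate at which earlier non-responders answer a later form. Assuming 20-40%:

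- Some data: 0.20 × 628 = 126 to 0.40 × 628 = 251 children
- Of these, both later forms offered again: 0.20 × 329 = 66 to 0.40 × 329 = 132 children

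**The case against.** The best defence is that the rule costs little where it counts. Day 1-4 fever comes from Q1, and the Per Protocol criterion in section 9.3 that names a questionnaire concerns Q1 only. A family without Q1 lacks the primary endpoint with or without the rule. The secondary endpoints carry no non-inferiority test (section 9.6). All of this stands.

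It also stands that continuing is not free. Under sections 6.3.3 and 6.3.4, Q2 and Q3 ask about events begun since the previous form was completed, so they need a different wording when that form is missing, and free text has to be coded by hand.

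A reader might go further than the text allows in five ways:

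- *That missing day 8 ends participation.* Section 4.6 refers to non-completion after a reminder, and 6.4 only removes late returns from the Per Protocol analysis. The defect is the undefined link between the two.
- *That the loss falls on sick or hospitalised children.* This is plausible, but parents who saw a reaction may equally be keener to answer. The protocol supports neither direction. The rule is the same in both groups, and section 8.1 says that parents are not told which product was given.
- *That serious events are lost.* Parents may contact the centre at any time (section 4.5), although that route is framed as help with questions, and known serious events are followed until resolved or stable (section 10.2.3). What ends is active prompting. The protocol describes no active follow-up of non-responders.
- *That the rule lowers the complete datasets in section 8.3.* That count requires all questionnaires to be completed. A family that has missed one is outside it, whatever is sent later.
- *That all 900 non-completers are affected.* Those who miss only Q3 lose nothing through the rule, and some of the 900 may be true withdrawals, whom no change would bring back.

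What the defence does not supply is a reason for the rule. The protocol gives none, and nothing in the timetable requires that Q2, due on day 14, be cancelled because Q1 was not returned.

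**Conclusion.** The point holds within limits. Section 4.6 ends active follow-up of registered families that have not withdrawn after a single unanswered form, at a moment it does not define, and it is not reconciled with section 6.4. The effect is avoidable missing data in the day 5-28 secondary endpoint and less active solicitation of serious events.

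The size rests on an assumed split of the planned loss. With equal proportional loss at each form, about one starter in six is denied a later questionnaire; the plan's figures alone allow anything from none to a quarter. The share that could be regained rests on a further assumption, the 20-40% response. The conclusion about the rule itself depends on neither. It does not extend to the primary comparison or the sample size, and a distortion between old and new vaccine cannot be inferred from the protocol.

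**What to change.** - Change section 4.6 so that every registered family that has not withdrawn receives Q2 and Q3, whether or not an earlier form came back.
- When an earlier form is missing, have Q2 and Q3 ask about events since vaccination, with onset date, instead of since the previous form.
- Keep late or retrospective day 1-4 answers out of the Per Protocol set, but use them in sensitivity analyses and safety listings.
- Align section 4.6 with section 6.4: say on which day a form counts as not returned, and that a late return affects only the analysis set.

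The cost is a short protocol change, a branch in the web forms, up to two more automated e-mails with their reminders per non-responding family, some extra free-text coding, and longer recall for the answers so obtained. The planned numbers stay as they are.

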5.1 Primary study parameter

Proportions of children with fever (rectally measured body temperature of $\geq 38.0^{\circ}\text{C}$) within 4 days after vaccination with NeisVac-C® and MMR.

5.2 Secondary study parameter(s)

Proportions of children with solicited other systemic and local reactions within 4 days after vaccination with NeisVac-C® and MMR.

The occurrence of the following reactions will be asked actively:

Local (injection site) reactions at the NeisVac-C® and/or MMR injection site

- redness, warmth, pain, swelling, induration, blue, itch

General (systemic) reactions

- rash
- decreased appetite
- less sleeping
- listlessness
- sleepiness/somnolence
- vomiting
- diarrhea
- (febrile) seizures

In addition a free text field is available so that symptoms not listed above can be reported.

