6.3 Assessments / collection of data

6.3.1 Preregistration and registration

Upon receipt of the first letter parents may pre-register for the study by reporting their email address and scheduled vaccination date. At this date, Lareb will send them an email with a link enabling the parents to register for the study.

After vaccination, parents are given a flyer with information about the study, and how to sign-up for the study (web address and study specific access code).

The following data are requested.

- general data

1. are MenC and MMR vaccines administered both? If only one, or more than 2, vaccines were given, the child cannot further participate.
2. reporting code
3. date of vaccination
4. batch numbers of administered vaccines (to be recorded at baby clinic)
5. injection sites of administered vaccines (arm/leg/left/right) (to be recorded at baby clinic)
6. registration of email address. Per email address, only one child can participate. For more children in a household/family (twins, triplets,..) separate email addresses are required.
7. accept Lareb privacy rules yes/no. Only proceed if ticked: yes.

- data of reporting parent and child

1. confirm email address
2. child: date of birth
3. child: sex
4. child: height at time of vaccination
5. child: weight at time of vaccination
6. baby clinic: place and street address (choose from list).

- base line data

1. medical history, did your child have: ... (tick if applicable)
 - infections,
 - coughing/dyspnea,
 - skin rash,
 - hypersensitivity or allergy,
 - vomiting and/or diarrhea,
 - other: please specify ...,
 - none of the above.

- concomitant medication

1. Does your child use any medication: if yes: specify the medicine, dose, start date and stop date if applicable

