6.3.2 Questionnaire 1 (4 days after vaccination)

Start question: did your child experience an adverse reaction/event: Y/N.

If N: have other medicines been used: click to add

If Y: which adverse events have occurred

- injection site reaction, if yes
 - o where did the reaction occur: one or both sites: specify arm/leg/left/right
 - o further questions per injection site
 - tick symptoms: red, warm, pain, swelling, indurated patch, blue, itch, other: please specify
 - size: largest possible diameter in centimeters (rounded upwards)
 - onset time after injection
 - treated, if yes specify
 - recovery status, if recovered: when
 - size will be categorised by diameter <2 cm: mild, 2-5 cm: moderate, >5 cm: severe
- fever, if yes
 - what was temperature (max value, rectally measured): __, __°C
 - onset time after injection
 - treated, if yes specify
 - recovery status, if recovered: when
 - impact as experienced by parents, graded as: not-mildly-moderately-very
- skin rash
 - please describe ...,
 - onset time after injection
 - treated, if yes specify
 - recovery status, if recovered: when
 - impact as experienced by parents, graded as: not-mildly-moderately-very
- less appetite
 - onset time after injection
 - treated, if yes specify
 - recovery status, if recovered: when
 - impact as experienced by parents, graded as: not-mildly-moderately-very
- sleeping less
 - please describe ...,
 - onset time after injection
 - treated, if yes specify
 - recovery status, if recovered: when
 - impact as experienced by parents, graded as: not-mildly-moderately-very
- sleeping more/somnolence
 - onset time after injection
 - treated, if yes specify
 - recovery status, if recovered: when
 - impact as experienced by parents, graded as: not-mildly-moderately-very
- listlessness
 - onset time after injection
 - treated, if yes specify
 - recovery status, if recovered: when
 - impact as experienced by parents, graded as: not-mildly-moderately-very

- vomiting
 - onset time after injection
 - how often
 - treated, if yes specify
 - recovery status, if recovered: when
 - impact as experienced by parents, graded as: not-mildly-moderately-very
- diarrhea
 - onset time after injection
 - how often
 - treated, if yes specify
 - recovery status, if recovered: when
 - impact as experienced by parents, graded as: not-mildly-moderately-very
- (febrile) seizures
 - please describe:
 - what was temperature at the time of the seizure:
 - onset time after injection

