7.2 Description of route of administration and dosage

NeisVac-C® will be injected intramuscularly (one dose is 0,5 ml). MMR will be injected subcutaneously (one dose is 0,5 ml, after reconstitution).

Injection sites are not prescribed in this protocol. The baby clinic personnel is asked to follow their usual practice. Neither the various organisations of child health care, nor the National Immunisation Programme prescribe the injection sites.

After injection, baby clinic staff is asked to write down which vaccine is injected where, and which batch numbers were used. Parents are asked to enter these data into the questionnaires.

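### Section 5.2 does not say at which injection site local reactions are compared, and as worded it permits an any-site count that would pull the relative risk towards 1

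*Protocol*

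**What the plan says.** Protocol section 5.2 gives the secondary parameter as "Proportions of children with solicited other systemic and local reactions within 4 days after vaccination with NeisVac-C® and MMR". The unit is the child, and no injection site is named. The next sentence, "The occurrence of the following reactions will be asked actively", opens a list whose local part is headed "Local (injection site) reactions at the NeisVac-C® and/or MMR injection site". The synopsis and sections 2.2, 9.4 and 9.6 do not narrow the site any further.

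Data collection is by site. Questionnaire 1 (section 6.3.2) asks "where did the reaction occur: one or both sites: specify arm/leg/left/right" and then puts "further questions per injection site" on symptoms, size, onset, treatment and recovery. The link from vaccine to site is also recorded: under section 7.2, "baby clinic staff is asked to write down which vaccine is injected where, and which batch numbers were used", and parents enter this at registration (section 6.3.1). Section 7.2 adds "Injection sites are not prescribed in this protocol"; clinics follow their usual practice.

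On analysis, section 9.4 makes the secondary endpoints descriptive. Section 9.6 has them analysed in the same way as fever, that is by a log-link model giving relative risks, but without a non-inferiority decision.

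**The concern.** The study compares two sources of NeisVac-C bulk material. MMR is the same in both groups, and its batches are not tied to group (sections 7.1 and 7.4). A reaction confined to the MMR site therefore says nothing about the change of production site. For fever, section 1.1 explains how the four-day window keeps a NeisVac-C effect apart from an MMR effect. For local reactions separation is more direct, because the two vaccines go into different sites, yet the parameter is not tied to either one.

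If the wording were applied literally, a real increase at the NeisVac-C site would appear as a smaller relative risk and could be read as comparability. Leaving the site open also allows that choice to be made after the data have been seen.

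**Working it through.** The protocol states no local-reaction rate, margin or power, so there is no figure to reproduce. The calculation shows only how large the effect of an any-site count could be.

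**Assumed inputs (none from the protocol).** p = rate at the NeisVac-C site with the old product; m = rate at the MMR site, equal in both groups; true relative risk at the NeisVac-C site = 1.5. The value 1.5 is borrowed from the fever margin for illustration only.

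**Formula, sites independent within a child.**

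- Old product, any site: 1 - (1 - p)(1 - m)
- New product, any site: 1 - (1 - 1.5p)(1 - m)
- Any-site relative risk: the second divided by the first
- Any-site difference: 0.5p(1 - m), against 0.5p at the NeisVac-C site

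| p | m | Old, any site | New, any site | Any-site RR | Any-site difference | Difference at NeisVac-C site |
|---|---|---|---|---|---|---|
| 10% | 5% | 14.5% | 19.25% | 1.33 | 4.75 points | 5 points |
| 10% | 10% | 19% | 23.5% | 1.24 | 4.5 points | 5 points |
| 10% | 20% | 28% | 32% | 1.14 | 4 points | 5 points |
| 10% | 30% | 37% | 40.5% | 1.09 | 3.5 points | 5 points |
| 20% | 10% | 28% | 37% | 1.32 | 9 points | 10 points |
| 20% | 20% | 36% | 44% | 1.22 | 8 points | 10 points |
| 30% | 5% | 33.5% | 47.75% | 1.43 | 14.25 points | 15 points |

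Over p of 10-30% and m of 5-30%, the any-site relative risk runs from 1.09 (p = 10%, m = 30%) to 1.43 (p = 30%, m = 5%). The share of the excess relative risk that is lost is 1 - (RR - 1)/0.5. At p = 20%, m = 10% this is 1 - 0.321/0.5 = 36%; at p = 10%, m = 20% it is 1 - 0.143/0.5 = 71%.

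**No overlap.** If no child reacts at both sites, the any-site rates are p + m and 1.5p + m, and the absolute difference does not shrink at all. The relative risk still falls: at p = m = 10% it is 25%/20% = 1.25, against 1.24 under independence.

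**Detectability.** This uses 1215 per group, the protocol's number for fever, and a two-sided 5% comparison of two proportions that ignores clustering by clinic. At p = m = 10% the power is 96% at the NeisVac-C site. For the any-site count it is 77% (independent sites) to 84% (no overlap).

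**Separability.** Sections 6.3.1, 6.3.2 and 7.2 together supply the site of each vaccine and the site of each reaction. Location is held only as arm or leg, left or right, so attribution may fail when both vaccines went into the same limb.

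**The case against.** The strongest reply is that the quoted line is a sub-heading in a list of what parents are asked, not an analysis rule. On that reading, the and/or says only that reactions at either site are solicited. This stands in part: a reader might infer that the protocol has fixed a pooled endpoint, and it has not. No sentence says that an MMR-only reaction counts towards a single local endpoint. But section 5.2 is where the secondary parameters are set, and it offers no other description of the local one.

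A reader might also infer that information is lost. It is not. Collection per site, with size graded under the per-site questions, points if anything towards a presentation by site, and the data stay separable whichever table is drawn first.

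The statistical analysis plan, which is not at hand, may settle the tabulation, and table layout properly belongs there. Which site makes a child an event is closer to endpoint definition, which section 5.2 takes up and leaves open.

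The relative risk is also the scale on which dilution looks worst. Section 9.4 commits to counts and percentages per group, where most of the excess would remain visible. That is correct and limits the weight of the point.

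Finally, parents are not told which product was given (section 8.1), so reporting driven by knowledge of the product is limited. Using the MMR site as an internal check is therefore a useful addition, and its absence is not an error. It retains some value because clinics are the units assigned (section 8.2) and may differ in how reactions come to be reported.

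**Conclusion.** The point holds as a minor one about wording. Section 5.2 permits an any-site local endpoint, and nothing in the protocol ties the comparison to the NeisVac-C site. If the endpoint were counted that way, a true relative risk of 1.5 would appear as about 1.09 to 1.43, while the absolute difference would shrink by the factor (1 - m), that is by 5% to 30% of its size. These figures rest on assumed reaction rates and on independence of the two sites within a child; they illustrate the effect and are not estimates for this study.

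The documents do not support a claim that the sites will be pooled, or that the study's conclusion is at risk. The secondary endpoints carry no non-inferiority decision, and the primary comparison of fever is unaffected.

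**What to change.** In sections 5.2 and 9.6, state that solicited local reactions are compared between products at the NeisVac-C injection site, by symptom and size category, using the per-site answers and the vaccine-to-site record already collected. Report MMR-site reactions in a separate table as an internal check: a relative risk away from 1 there would point to reporting or clinic differences, not to the product. List reactions that cannot be assigned to one vaccine, because both went into the same limb, as a third category. An any-site figure may be kept as supporting description.

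The cost is about two sentences and a few table rows, with no new data, visits or staff. The one drawback is that some same-limb reactions will remain unassigned; showing their number in each group makes that visible.
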